Cohort 1 will enroll subjects with malignant thyroid tumors with HRAS mutations, independently of thyroid histology. Any subject with a non-hematological HRAS mutant tumor who meets eligibility criteria may be enrolled in the first stage of Cohort 2. Subjects with HNSCC, salivary malignancies and urothelial carcinomas may be more frequently enrolled in Cohort 2 due to the relatively high rate of HRAS mutations in these indications; however, enrolment is not limited to these tumor types. Subjects with malignant thyroid tumors with HRAS mutations will only be enrolled in cohort 1. Based on the anti-tumor activity observed during stage 1 of cohort 2, the protocol was amended (Amendment 3) to restrict enrollment in stage 2 of Cohort 2 to subjects with HNSCC with HRAS mutations only.

Cohort 3 will enroll subjects (N=20 evaluable) who have SCC with HRAS mutations. The purpose of this cohort is to explore tipifarinib's anti-tumor activity in HRAS mutation positive SCCs independent of tissue origin.

Tipifarnib will be administered at a starting dose of 600 mg, po, bid daily on days 1-7 and 15-21 of 28-day treatment cycles. In the absence of unmanageable toxicities, subjects may continue to receive tipifarnib treatment for up to 12 months in the absence of disease progression and unmanageable toxicity. Treatment may continue beyond 12 months upon agreement of the Investigator and Sponsor.

Tumor assessments will be performed at screening and approximately every 8 weeks for the first 6 months (cycles 2, 4, 6) and then every 12 weeks (cycles 9, 12, 15, etc.) until disease

progression, starting at the end of Cycle 2. Additional tumor assessments may be conducted if deemed necessary by the Investigator or for a confirmation of an objective response. Subjects who discontinue tipifarnib treatment for reasons other than disease progression must continue tumor assessments until disease progression, withdrawal of subject's consent to study procedures or initiation of another anticancer therapy.

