- 9. Tumor assessments: Appropriate spiral CT with contrast (preferred method) or MRI scans will be conducted at screening and Day 22 ± 5 days of every even cycle for the first 6 months (Cycles 2, 4, 6) and then every 12 weeks (Cycles 9, 12, 15, etc.) until disease progression or subject's End of Treatment visit. Scans at the End of Treatment visit will be performed if not done within the prior 8 weeks unless additional anticancer therapy has been initiated or if a tumor assessment is required for the confirmation of response. Subjects who discontinue treatment for reasons other than disease progression should continue tumor assessments until disease progression, withdrawal of subject's consent or initiation of another anticancer therapy. If subject is allergic to IV contrast, MRI scans or non-contrast CT may be used. The imaging schedule (every 8-12 weeks) should be maintained regardless of dosing delays or additional imaging assessments performed. Tumor scans will be reviewed by the clinical sites. Tumor assessments may be conducted locally for convenience; however, efforts should be made to decrease the variability of the assessments. An independent review of tumor scans may be conducted if deemed necessary by the Sponsor for the assessment of the efficacy of tipifarnib. Copies of tumor images must be de-identified of subject's personal information at the clinical sites and provided to the Sponsor or its designee if an independent review is requested by the Sponsor.
- 10. Subjects will receive tipifarnib starting at 600 mg orally bid with food on days 1-7 and 15-21 of 28 day treatment cycles.
- 11. Buccal swabs will be collected at screening for CXCL12 SNP testing and as a control sample for the analysis of tumor mutations using kits provided by the Sponsor. If swabs are not collected during screening for any reason, collection can be conducted at any time during the study. Detailed buccal swab collection, storage and shipping procedures will be provided in a separate lab manual.
- 12. An End of Treatment visit will be conducted within 30 days (+/- 7 days) from the last dose of tipifarnib or immediately before the initiation of any other anticancer therapy.
- 13. Complete physical exam will be performed at screening within 14 days of first administration of study drug and at the End of Treatment visit. A symptom-based physical exam will be conducted on Day 1 of every treatment cycle.

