Tumor assessments will be performed at screening and approximately every 8 weeks starting at the end of cycle 2 for the first 6 months (cycles 2, 4, 6) and then every 12 weeks (cycles 9, 12, 15, etc.), or sooner if deemed necessary by the Investigator, and will continue until disease progression. A tumor assessment will be performed upon treatment discontinuation (End of Treatment visit) if the reason for discontinuation is other than disease progression and no tumor assessment was performed in the prior 8 weeks, or a tumor assessment is required for the confirmation of response to treatment. Subjects who discontinue treatment for reasons other than disease progression must continue tumor assessments until disease progression, withdrawal of subject's consent or initiation of another anticancer therapy. Determination of objective tumor response will be performed by the Investigator. However, tumor images may be de-identified of subject's personal information at the clinical sites and collected by the Sponsor or designee to undergo an external independent radiological review if the sponsor deems it necessary for the final assessment of the efficacy of the treatment. If an independent radiological review were to be conducted, reviewers would be blinded to Investigator's tumor response assessments. An independent review committee charter would be generated to provide the specific procedures that would be filed with IRB/ECs and regulatory authorities.

Subjects with a solitary site of disease who have experienced a response may be considered for surgical resection. Subjects with a Partial Response (PR) and residual disease after salvage surgery are eligible to continue on study therapy.

Upon disease progression, all subjects in the study cohort will be followed approximately every 12 weeks for survival and the use of subsequent therapy until either death or 12 months after accrual in the subject's study cohort has been completed, whichever occurs first. Information on survival and subsequent anticancer therapy may be collected by phone.

All subjects will be followed-up for safety during treatment and up to approximately 30 days (30 +/- 7 days) after treatment discontinuation or until immediately before the initiation of another anti-cancer therapy, whichever occurs first. Additional follow up may be implemented until the

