10.1 Efficacy Variables

Radiological and/or physical assessments of the tumor lesions, and evaluations of relevant tumor markers (e.g. CA125, PSA, CA19-9, CA27.29, thyroglobulin, anti-thyroglobulin antibodies, calcitonin and CEA, to be assessed at the judgment of the Investigator) will be made at screening (4 weeks before the first study drug administration), at the end of cycle 2 and at approximately 8 week intervals thereafter until disease progression. Additional tumor assessments may be conducted at the judgment of the Investigator. Subjects who discontinue treatment for reasons other than disease progression must continue tumor assessments until disease progression, withdrawal of their consent to study procedures or initiation of another anticancer therapy. Efficacy assessments may also be conducted at treatment discontinuation (End of Treatment visit) if the reason for the treatment termination is other than disease progression and a tumor assessment was not done within 8 weeks before treatment discontinuation (assessment must be

conducted before additional anti-tumor therapy is started). Scans at the End of Treatment visit will be also conducted if required to confirm response to treatment.

Lesions to be included in the tumor assessments should follow RECIST v1.1. Spiral CT scan with a contrast agent is the preferred imaging method. Tumor assessment with spiral CT scans should be performed as appropriate. Subjects with contrast allergy may use non-contrast CT or MRI, whichever is required to adequately assess all disease.

Objective response (complete response and partial response) as determined by the subject's best tumor response, duration of response, and time to progression will be assessed using RECIST v1.1. Confirmation of response is required.

In addition to Investigator's tumor response assessment, a central independent review tumor response assessment may be performed if the sponsor deems it necessary for the final assessment of the efficacy of the treatment. If an independent radiological review were to be conducted, reviewers will be blinded to the Investigator's efficacy assessments. The sponsor, in consultation with the investigators, may initiate this independent review at any time during the trial. In that case, an independent review committee charter would be generated to provide the specific procedures that would be filed with IRBs/IECs and regulatory authorities prior to their initiation.

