11.7 Post Treatment Follow up

Follow up visit(s) are required only for subjects who terminated treatment for reasons other than death or disease progression and should occur approximately every 8-12 weeks until disease progression or death, whichever occurs first. If the subject initiates a new anticancer therapy without evidence of disease progression by RECIST v1.1, tumor assessments should continue

until there is evidence of disease progression unless withdrawal of subject's consent to study procedures.

The assessments to be conducted at these visits are:

- Radiographic Imaging: to be performed if not done within the prior 8 weeks or if a tumor assessment is required for the confirmation of response.
 - o CT scan with a contrast agent is the preferred imaging method and the same technique should be used at baseline and post-treatment assessments.
 - o In subjects with HNSCC, CT scan coverage at screening should encompass scans of the neck (including the skull base), chest and abdomen (including the liver and adrenals). Any other areas of disease involvement should be scanned based on the subject's signs and symptoms.
 - o In subjects with other solid tumors, scan coverage should be appropriate to ensure that all areas of disease involvement are scanned.
- Assessments of AEs and concomitant medications may also be conducted if AEs were not resolved at the time of the End of Treatment visit.

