9.2. Exploratory Efficacy Analyses

The duration of objective response (DOR) will be calculated for subjects who achieve CR or PR. For such subjects, the DOR is defined as the number of days from the start date of PR or CR (whichever response is achieved first) to the first date that progressive disease is objectively documented. Disease progression will be determined by the Investigator using RECIST (version 1.1). The DOR will be right-censored at the date for subjects who achieve CR or PR and meet 1 of the following conditions: 1) when non-protocol anticancer treatment started before documentation of disease progression, 2) when death prior to documented disease progression or documented disease progression after more than 1 missed disease assessment visit, or 3) when alive and does not have documentation of disease progression before a data analysis cutoff date. (Therefore, analysis cutoff date will be used as the censoring date).

Progression free survival (PFS) will be defined as the time (in months) from first dose (Cycle 1 Day 1) to either first observation of progressive disease or occurrence of death due to any cause within 126 days (approximately 2 time intervals for tumor assessments) of either first administration of tipifarnib or the last tumor assessment. Observation of progressive disease can be by either documented radiographic progression (i.e., scan results) or documentation of symptomatic or clinical progression agreed upon and documented by investigators. In subjects without a progression date or with a death date more than 126 days after the first administration of study drugs or the last tumor assessment, the PFS time should be censored on the date of last tumor assessment or date of first administration of study tipifarnib. PFS analyses should consider tumor assessments after treatment discontinuation or metastatic surgery.

The DOR and PFS, will be summarized descriptively using the Kaplan-Meier (KM) method. The 25th, 50th, and 75th percentiles of the Kaplan-Meier distribution will be used to describe the median response duration and median PFS.

The median DOR and PFS and corresponding pointwise 95% confidence interval will be displayed by cohort for the FAS population and for the PP population, and for the subgroups.

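### Protocol 11.7 continues scans after new anticancer therapy, five other places stop them, and PFS has no new-therapy rule, so exploratory PFS in early switchers depends on site practice

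*Protocol*

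**What the plan says.** **When scans end.** The subjects in question have stopped tipifarnib for a reason other than progression.

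- Protocol 11.7 (Post Treatment Follow up): "If the subject initiates a new anticancer therapy without evidence of disease progression by RECIST v1.1, tumor assessments should continue" and then "until there is evidence of disease progression unless withdrawal of subject's consent to study procedures". Withdrawal of consent is the only exception.
- Protocol 8.1: such subjects "must continue tumor assessments until disease progression, withdrawal of subject's consent or initiation of another anticancer therapy". SAP 4.1 has the same rule.
- Protocol Table 1, note 9: they "should continue tumor assessments until disease progression, withdrawal of subject's consent or initiation of another anticancer therapy".
- Protocol Synopsis, study design: the end points besides progression are "withdrawal of subject's consent to study procedures or initiation of another anticancer therapy".
- Protocol 10.1: likewise "withdrawal of their consent to study procedures or initiation of another anticancer therapy".

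**How PFS is defined.** Protocol 12.2.1 and SAP 9.2 count progression, or death within 126 days of first dose or of the last tumor assessment. Subjects with no progression date, or with a later death, are censored at the last assessment (or at first dose). New therapy is not mentioned. SAP 9.2 also accepts investigator-documented clinical progression as an event, and adds: "PFS analyses should consider tumor assessments after treatment discontinuation or metastatic surgery".

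**How duration of response is defined.** In the same sections it is right-censored "when non-protocol anticancer treatment started before documentation of disease progression".

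**Sensitivity analyses.** Protocol 12.2.1 refers PFS sensitivity analyses to an FDA guidance without writing out a rule. SAP 9.2 does not carry this over. The sensitivity analysis it describes concerns how the median is estimated.

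**The concern.** A site cannot follow both scan rules for the same subject. Normally the analysis rule would neutralise such a conflict, but the PFS rule depends on whether a progression date exists and when the last scan was taken. Both depend on whether the site kept scanning. The choice between censoring and an event is then made by site practice and not by the analysis plan. The Kaplan-Meier curve may mix two quantities: time to progression up to a switch, and time to progression through whatever treatment followed.

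Duration of response shows that the plan recognises new therapy as an event needing a rule, yet PFS has none and no reason is given for the difference.

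The problem also reaches the optional comparison of PFS on tipifarnib with PFS on prior therapy (SAP 9.2), which would yield a P value. Under SAP 8.3, prior-therapy PFS without a progression date ends at the start of tipifarnib, the next drug. Tipifarnib PFS under Protocol 11.7 can run on through the next drug, so the two sides may be measured differently.

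**Working it through.** The plan states no figure for this point, so there is none to reproduce. The check compares the texts, follows one subject through them, and then gauges the size under stated assumptions.

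**1. The texts.** Five places stop scans at new therapy (Synopsis, Table 1 note 9, 8.1, 10.1, SAP 4.1) and one continues them (11.7). All six address subjects off treatment without progression, so the conflict is direct.

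**2. One subject (assumed).** Scans at nominal 8-week points, days 56 and 112, show no progression. Tipifarnib stops, new therapy starts on day 130, and a day-168 scan would show progression. Months = days / 30.4375 (SAP 7.1), counted from first dose (SAP 9.2).

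- Stop rule: no day-168 scan. Without clinical progression or an early enough death, PFS is censored at 112 / 30.4375 = 3.68 months.
- Continue rule: event at 168 / 30.4375 = 5.52 months, with 168 − 130 = 38 days since the new drug started.

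An End of Treatment scan does not alter this. The day-112 scan is 130 − 112 = 18 days before the switch, inside both the 4-week window in Protocol 11.6 and the 8-week window in Table 1 note 9 and 8.1.

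**3. Deaths.** The 126-day window starts from the last scan, so it moves too. Change the example so that the day-168 scan is clean and the subject dies on day 250 with no scan in between. Under the stop rule 250 − 112 = 138 > 126, so PFS is censored at day 112. Under the continue rule 250 − 168 = 82 ≤ 126, so death is an event at day 250. A death by day 112 + 126 = 238 is an event under either rule.

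**4. Size (simulation; none of these inputs is in the documents).** Exponential time to progression with median 168 days, so hazard λ = ln 2 / 168. Exponential time to new therapy with hazard μ = λf / (1 − f), so that a fraction f switches before progression. Hazard ratio after the switch 0.5, 1 or 2. Scans at days 56, 112 and 168, then every 84 days. No deaths, complete follow-up, 100,000 subjects per scenario.

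| Switching f | Events per 30, continue | Events per 30, stop | 12-month PFS, stop | 12-month PFS, continue (HR 0.5 / 1 / 2) |
|---|---|---|---|---|
| 10% | 30.0 | about 26.5 | about 25% | 26.4% / 25.0% / 23.3% |
| 20% | 30.0 | 23.1 | about 25% | 28.6% / 24.9% / 21.4% |
| 30% | 30.0 | 19.8 | about 25% | 30.5% / 25.0% / 19.5% |

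Events under the stop rule fall slightly below 30(1 − f) = 27, 24 and 21, because a progression that occurs before the switch but would be detected only afterwards is also lost. The largest shift in 12-month PFS is 30.5 − 25.0 = 5.5 points. For scale, a proportion of 25% in 30 subjects (the planned HNSCC number) has standard error √(0.25 × 0.75 / 30) = 7.9 points.

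**The case against.** The strongest reply is that little hangs on this. PFS is exploratory and summarised descriptively, the comparison with prior therapy is optional, and the two-stage decisions rest on response rate. The simulated shifts are smaller than one standard error at n = 30. They compare all sites stopping with all sites continuing, so mixed practice should differ less. If the new drug leaves the hazard unchanged, the curves agree and only the event count differs. All of this stands and limits the severity.

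Four stronger readings are tempting, and the documents do not support them.

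- *Every subject who switches before radiographic progression is affected.* SAP 9.2 also counts clinical progression, and deaths within 126 days of the last assessment. A switcher may already have an event under either scan rule.
- *The SAP tells the analyst to use scans taken after new therapy.* The sentence quoted from SAP 9.2 concerns stopping tipifarnib, or surgery. It fits the stop rule equally well, since that rule requires scans between discontinuation and the new drug.
- *No sensitivity analysis was planned.* Protocol 12.2.1 plans some by reference to a guidance. Whether they cover new therapy cannot be seen from the documents. The supportable gap is that no rule is written out and the SAP drops the reference.
- *Duration of response is already censored at the last evaluable scan, so PFS need only copy it.* SAP 9.2 does not fix that date. Its wording is incomplete, and its closing parenthesis names the analysis cutoff.

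It is also fair that censoring at new therapy and disregarding new therapy are both legitimate definitions. The defect is that neither is stated.

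**Conclusion.** The point holds in a limited form. The scan instructions contradict each other, and the PFS definition does not resolve the conflict. For subjects who stop tipifarnib without radiographic or clinical progression and then start new therapy, PFS depends on which section the site followed. Deaths more than 126 days after the last scan taken under the stop rule can be affected in the same way.

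The documents do not say how many such subjects there are. The effect on the curve is probably modest: at most about 5.5 points in 12-month PFS in the scenarios tried, which rest on assumed progression times, switching rates and hazard ratios. The loss of events is larger, from 30 to about 20 per 30 subjects at 30% switching. The endpoint is exploratory, and nothing here shows an effect on the primary response-rate analysis. The change should be made, but the trial's main conclusion does not depend on it.

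**What to change.** 1. **One scan rule.** Reconcile Protocol 11.7 with the Synopsis, Table 1 note 9, 8.1, 10.1 and SAP 4.1.
2. **One PFS rule in SAP 9.2 for new anticancer therapy**, giving the same value whichever scan rule a site followed. Censoring at the last evaluable assessment before new therapy does this: the example subject is censored at day 112 either way. It is also in line with duration of response recognising new therapy. The rule should say whether a death after the switch but within 126 days of that assessment still counts. Either answer removes the site dependence, because the reference scan precedes the switch.
3. **A sensitivity analysis** of PFS regardless of new therapy, noting that scans not taken limit it.
4. **The alternative.** If the sponsor prefers PFS regardless of new therapy as the main analysis, the SAP should say so and the five places that stop scans must be changed instead. Rewording cannot recover scans already missed.

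The cost is protocol wording, one censoring rule and one extra table. Table 1 already collects anticancer treatment at follow-up, and SAP 9.3 lists subsequent therapy. The downside is some additional censoring, possibly informative if subjects switch because of toxicity or deterioration. SAP 4.0 (January 2021) follows the April and September 2020 data cuts named in SAP 7.2, so the change should be recorded, with its reason, as made after those cuts.

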11.7.1 Follow Up after Disease Progression

Upon disease progression, all subjects will be followed approximately every 12 weeks for survival and the use of subsequent therapy until either death or 12 months after accrual in the subject's study cohort has been completed, whichever occurs first. Information on survival and subsequent anticancer therapy may be collected by phone.

12 STATISTICAL METHODS

This section outlines the statistical analysis strategy and procedures for the study. Specific details of the primary and key secondary analyses will be provided in the Statistical Analysis Plan (SAP). If, after the study has begun, but prior to the final analysis, important changes are made to the protocol that affect principal features of the primary or key secondary analyses, then the protocol and/or SAP will be amended, as appropriate. Any other changes made to the planned analyses after the protocol and SAP have been finalized, along with an explanation as to when and why they occurred, will be listed in the Clinical Study Report (CSR) for the study. Post hoc exploratory analyses will be clearly identified in the CSR.

